2.2 Name and Description of the Investigational Agent

2.2.1 Preclinical Data

The investigational treatment in this study, HLA vaginal insert, Revaree (brand name), is a FDA-approved class II medical device. It is a 2g vaginal insert that contains 5mg of HLA sodium salt and a base of semi-synthetic glycerides. It is an insert that does not require an applicator and should be placed in the vagina while laying down twice weekly. HLA in different formulations is currently used in disciplines such as ophthalmology and orthopedic surgery. As explained below, it is an extremely well tolerated medication with little to no side effects.

In a study of rats randomly assigned to oophorectomy plus placebo, oophorectomy plus vaginal HLA gel, or sham oophorectomy, it was found that HLA resulted in a reversal of vaginal atrophy with no associated increase in uterine weight (7). This study is particularly promising because it not only shows the reversal of atrophy but also it suggests that HLA has no effect on uterine weight (a proxy for endometrial lining) which is a feared complication of unopposed systemic estrogen therapy.

2.2.2 Clinical Data to Date

One of the earliest human studies examining the potential application of HLA for GSM symptoms as a non-hormonal alternative comes from Italy in 2006 (8). A pilot study of just 10 patients was initially performed to assess the safety profile of use of HLA gel on the vulva for GSM symptoms for 30 days. No side effects or adverse events were noted between the start and end of the usage period. No lab abnormalities were found aside from a ‘slight increase’ in monocyte percentage (9 to 13%) between the start and end, which the investigators deemed to be unrelated to the HLA treatment. Subsequently, a larger trial of 100 post-menopausal women was conducted by the same group of investigators. In this cohort, HLA was applied vaginally and studied over a period of 12 weeks. Using the visual analog scale (VAS) for GSM symptoms—specifically vaginal dryness, itching, burning, and dyspareunia—clinically significant improvement was noted from baseline to the end of the study period. Again, no adverse events or even side-effects were noted for the gel usage.

In a similar study from Italy, an open trial of 150 post-menopausal women were given a vaginal insert that contained HLA, vitamin E, and vitamin A to use for four weeks (9). Subjective and objective vaginal markers were compared over the four weeks and significant improvement was observed in the primary endpoint of vaginal dryness as compared to baseline with no side-effects to the HLA insert reported. It is important to note that while the HLA insert used in the cited study is different than the one proposed for this study, it used the same dose of HLA, 5mg, as found in this study’s HLA formulation.

An open RCT conducted in China in 2013 comparing vaginal HLA gel to vaginal estriol cream confirmed HLA’s overall efficacy and safety profile (10). Four mild adverse events were noted relating to HLA gel use. On laboratory testing, two patients were found to have vulvovaginal candidiasis and one patient was found to have bacterial vaginosis. These three patients had no symptoms, required no intervention, and the infections self-resolved. Only one patient was found to have symptomatic vulvovaginal candidiasis and was treated with no complications.

CONFIDENTIAL

This material is the property of the NYU School of Medicine and Langone Medical Center. Do not disclose or use except as authorized in writing by the study sponsor
Interventional Template Version: 11 January 2019

A small, recent study in Iran also noted the non-inferiority of vaginal HLA as compared to vaginal estrogen cream for symptomatic GSM (11). The study found that both treatment groups improved compared to baseline in dryness, itch, maturation index, pH, and a composite score of vaginal symptoms. However, only the HLA group showed improvement in symptoms of urinary incontinence. Further, improvement in the HLA group was significantly greater than the estrogen group for dryness, maturation index, and composite score. Meanwhile, a Turkish study found the opposite—vaginal estradiol tablets were more effective on improving vaginal symptoms as compared to vaginal HLA tablets, but both treatments still significantly improved all vaginal symptoms studied (12).

In summary, the clinical data to date on this topic comes from international studies comparing different vaginal HLA formulations to different vaginal estrogen formulations. However, all studies showed a safe usage profile of vaginal HLA, with only one clinically symptomatic fungal infection that required treatment.

2.2.3 Dose Rationale (if applicable)

In the US, the only dosage available for a vaginal insert preparation of HLA is 5mg, to the author's best knowledge. As noted above, some international studies have used this dosage with good safety profiles.

2.3 Rationale

GSM is a condition whose current standard of care is primarily hormone-based treatment. With patients being weary of using hormonal-based therapies and some patients being unable to receive such therapies even if willing, non-hormonal, safe alternatives must be explored. As noted earlier, there are a few preliminary international studies that have shown that HLA may be a promising new therapy for GSM. HLA alone has been shown in multiple studies to improve GSM symptoms.

This study proposes comparing HLA to vaginal estrogen cream because if the goal is to offer non-hormonal alternatives to all GSM patients, new therapies must be weighed against the standard of care. Additionally, no studies to date have used the VSQ proposed in this study as a tool to assess symptomatic and quality-of-life improvement. The hypothesis of this study is that HLA will be equal to estrogen in improving symptoms, quality of life, and physical attributes of GSM as compared to vaginal estrogen cream.

Both vaginal HLA and vaginal estrogen cream will be dosed and administered as recommended by the manufacturer to allow for reliable and realistic comparison of both therapies.

As mentioned above, HLA is associated with infrequent and usually mild side effects. The control in this study, vaginal estrogen cream, while also considered safe and FDA-approved for GSM, may be associated with certain side effects that would warrant further medical treatment. For example, if a patient starts to experience vaginal bleeding while on vaginal estrogen, the normal work-up for post-menopausal bleeding will be initiated.

Last, the intervention period of 12 weeks was chosen to allow for adequate time for therapeutic effect. Vaginal estrogen therapy can offer symptomatic improvement after just three weeks of

CONFIDENTIAL

This material is the property of the NYU School of Medicine and Langone Medical Center. Do not disclose or use except as authorized in writing by the study sponsor
Interventional Template Version: 11 January 2019

use, but can take four to six weeks in some patients (16). Thus, 12 weeks will maximize vaginal estrogen's therapeutic effect, allowing for a proper comparison of a novel therapy.

2.4 Potential Risks & Benefits

2.4.1 Known Potential Risks

Regarding vaginal HLA usage, the only observed risk thus far has been a fungal or bacterial infection in four patients, three of which were asymptomatic and did not require intervention and the remaining one was treated with no complication (10). Otherwise no other adverse events have been noted in studies.

Regarding the vaginal estrogen cream in this study, on the package insert for Estrace (see attached hyperlink), the risks of local vaginal estrogen are not separated from oral hormone replacement therapy (HRT). The package insert states that the risks include thromboembolism, retinal thrombosis, heart attack, stroke, breast cancer, ovarian cancer, endometrial cancer, endometrial hyperplasia, hypercalcemia, gallbladder disease, and probable dementia. It also includes possible exacerbation of the following conditions: hereditary angioedema, hypothyroidism, asthma, endometriosis, diabetes mellitus, epilepsy, migraine, hypertriglyceridemia leading to pancreatitis, hypoparathyroidism, porphyria, systemic lupus erythematosus, and hepatic hemangiomas (19).

However, when examining vaginal dosing of estrogen formulations, first, the dose is significantly less than oral HRT. Second, the risks associated with oral HRT, as mentioned above, have not been found in studies examining different—comparable to Estrace—vaginal estrogens. The reported cases of endometrial hyperplasia, breast or endometrial cancer were no different than those prior to initiation of therapy (20-24). Third, circulating levels of estradiol have been shown to be minimal with low-dose vaginal estrogen creams, tablets and the estrogen ring (25). Thus, systemic effects from these low-dose topical therapies are felt to be extremely rare. The other concern with any unopposed estrogen is endometrial safety. There have been several large studies that have established endometrial safety of various low-dose formulations of vaginal estrogen (VagifemTM, EstringTM and conjugated estrogen cream at a dose of 0.3mg) (20-22). Therefore, with low systemic absorption and no significant increase in endometrial pathology with low-dose vaginal estrogen, it is generally thought that the use of progestins is not necessary to protect the endometrium (23).

Reactions reported in randomized controlled trials of vaginal estrogen include application site reaction, vaginal bleeding/spotting, breast changes/pain, abdominal bloating/cramps, nausea/vomiting, cervical secretion changes, headache/migraine, fluid retention, elevated blood pressure, mood changes, candidiasis, glucose intolerance, weight changes, libido changes, contact lens intolerance, vision changes, rash, melasma/choasma, hair loss and hirsutism. Despite this risk profile, vaginal estrogen is well tolerated in most patients and is the recommended treatment if first-line over-the-counter vaginal moisturizers and lubricants do not work.

Regarding the office visit, the only potential risk of vaginal tissue sampling may be minimal bleeding, for which local pressure will be applied. If a patient is on oral HRT within 6 weeks of the study, she will not be able to participate in this study.

CONFIDENTIAL

This material is the property of the NYU School of Medicine and Langone Medical Center. Do not disclose or use except as authorized in writing by the study sponsor
Interventional Template Version: 11 January 2019

2.4.2 Known Potential Benefits

The potential physical benefits of vaginal HLA insert discussed in detail above come from multiple international studies. They include improvement in symptoms (dyspareunia, itching, dryness, vaginal bleeding), vaginal maturation index, vaginal pH, and urinary symptoms secondary to GSM (8-13). Regarding the vaginal estrogen cream to be used in this study, estrace, is FDA approved for the treatment of vulvovaginal atrophy secondary to menopause. Additionally, studies examining similar formulations of vaginal estrogen have showed improvement in GSM symptoms (20-22).

Regarding potential psychological benefits, no study to date has examined vaginal HLA's impact on quality of life; it is included in the primary objective of this study. A study that compared a vaginal moisturizer to vaginal estrogen tablets—very similar to the control being used in this study—found there was significant improvement in the overall sexual function domain and overall Menopause Quality of Life scores in the vaginal estrogen group (17).

3 Objectives and Purpose

3.1 Primary Objective

The primary objective is to measure symptoms and quality of life for GSM in those randomized to vaginal HLA versus vaginal estrogen cream in a contemporary cohort.

3.2 Secondary Objectives (if applicable)

The secondary objective is to measure objective and physical attributes of GSM, as well as treatment compliance and retention in those receiving vaginal HLA or vaginal estrogen cream.

4 Study Design and Endpoints

4.1 Description of Study Design

This will be an open, randomized, active control, parallel design study. This is a pilot randomized trial to gain understanding of symptom and quality of life, physical measurements, and overall protocol administration. There are two study arms, HLA vaginal insert (investigational) and vaginal estrogen cream (standard of care). Participants will be recruited and treated at a single-center study. Both interventions will last for 12 weeks. There will be no protocol changes to either medication in this study. Randomization will not be stratified.

4.2 Study Endpoints

4.2.1 Primary Study Endpoints

The primary endpoint will be the change in the VSQ score, between the baseline visit and 12 week follow-up.

The VSQ is a 21-question survey developed in 2012 that specifically asks about GSM symptoms, their emotional impact, sexual impact, and life impact. Among 120 post-menopausal women, this questionnaire was found to have reliability and internal consistency (15). Most importantly, in the absence of a gold standard instrument to assess the quality of life impact of

CONFIDENTIAL

This material is the property of the NYU School of Medicine and Langone Medical Center. Do not disclose or use except as authorized in writing by the study sponsor
Interventional Template Version: 11 January 2019

GSM, this questionnaire is critical. It is more nuanced and disease-specific than VAS scoring, and thus far, an underutilized tool to understand the significant psychological impact of this disease. Because GSM is a symptom-driven disease and patients will likely adhere to a treatment plan if they perceive symptomatic improvement, this study's primary endpoint of treatment success will be measured by improvement in VSQ scoring.

4.2.2 Secondary Study Endpoints

The secondary study endpoints will include: the change in the FSI and VSI score from baseline to the 12 week visit, the change in the percentage of superficial squamous cells in the vaginal maturation index, the change in vaginal pH, the qualitative change in rugal fold appearance, and the change in VAS scoring for vaginal dyspareunia, itching, and dryness. These are well-studied measurement tools for GSM research and have been used in some combination in all of the studies cited earlier.

Vaginal pH in a postmenopausal woman is generally between 6.0 and 8.0, while an estrogenized vagina will have a pH of 3.5 to 4.5 (18). Thus, the change in pH can be a surrogate marker for the hormonal influence on vaginal epithelium.

VMI is a qualitative measure of hormonal influences on the vaginal epithelium. It measures the percentage of parabasal, intermediate, and superficial squamous cells appearing on a smear and is a valuable tool when comparing the changes in two samples of the same patient (14).

Patient global impression of improvement (PGI-I), a one question assessment, will also be asked at the follow up visit for overall patient satisfaction assessment.

4.2.3 Exploratory Endpoints

N/A

5 Study Enrollment and Withdrawal

5.1 Inclusion Criteria

In order to be eligible to participate in this study, an individual must meet all of the following criteria:

1. Postmenopausal status as defined by amenorrhea for ≥ 12 months or history of bilateral salpingo-oophorectomy or if the patient has had a hysterectomy and menopausal symptoms for > 1 year or FSH > 40
2. Symptoms of GSM
3. Pap smear screening as per ASCCP (American Society of Colposcopy and Cervical Pathology) guidelines. If Pap smear was indicated in last three to five years, it must be negative.
4. Capable of giving informed consent
5. Ambulatory
6. Capable and willing to follow all study-relation procedures

CONFIDENTIAL

This material is the property of the NYU School of Medicine and Langone Medical Center. Do not disclose or use except as authorized in writing by the study sponsor
Interventional Template Version: 11 January 2019

5.2 Exclusion Criteria

An individual who meets any of the following criteria will be excluded from participation in this study:

1. Use of any HRT (systemic or local) or raloxifene within six weeks of proposed start date
2. History of estrogen-sensitive tumor
3. Undiagnosed vaginal bleeding in the past 12 months
4. History of thromboembolic event
5. Currently have or have had liver problem
6. Bleeding disorder
7. Impaired mental status
8. Prior pelvic irradiation
9. Active vaginal infection
10. Any medical reason the investigator deems incompatible with treatment with vaginal estrogen

5.3 Vulnerable Subjects

No vulnerable subject populations based on federal regulations are included in this trial. Children and fetuses are not affected by this disease, pregnant women by definition are not post-menopausal, and prisoners are not treated as outpatients at any of the study sites. The elderly are potential vulnerable subjects; however they need to be included in our study population to make the results useful in clinical practice as the average age of menopause is 51.2 years old.

However, those who are no longer able to provide consent for themselves will be excluded.

5.4 Strategies for Recruitment and Retention

All patients seen at [name] office will be offered participation in this randomized controlled trial.

Informed consent will take place at [name] office. Patients will be asked personal demographic information. Only staff (attendings, fellows, residents, medical students,) involved in the study will have access to this information.

5.4.1 Use of DataCore/Epic Information for Recruitment Purposes

This study will not utilize EPIC or Data Core to identify subjects.

5.5 Duration of Study Participation

There is no pre-screening to visit one. After visit one, the patient will have a follow-up visit approximately 12 weeks later. There is no follow up required after the 12 week visit. Thus, the duration of study participation is 12 weeks.

5.6 Total Number of Participants and Sites

Recruitment will end when approximately 60 participants are enrolled at this single site at NYUMC. It is expected that approximately 60 participants will need to be enrolled in order to retain 40 evaluable participants at 12 weeks of follow up (an overall 33% drop out rate).

CONFIDENTIAL

This material is the property of the NYU School of Medicine and Langone Medical Center. Do not disclose or use except as authorized in writing by the study sponsor
Interventional Template Version: 11 January 2019

5.7 Participant Withdrawal or Termination

5.7.1 Reasons for Withdrawal or Termination

Participants are free to withdraw from participation in the study at any time upon request. An investigator may terminate participation in the study if:

- Any clinical adverse event (AE), laboratory abnormality, or other medical condition or situation occurs such that continued participation in the study would not be in the best interest of the participant
- The participant meets an exclusion criterion (either newly developed or not previously recognized) that precludes further study participation

5.7.2 Handling of Participant Withdrawals or Termination

Patients who withdraw or terminate participation in this study will be called and a follow-up office visit will be set up at 12 weeks regardless of their participation. If the patient refuses to come in, a phone call will be made to discuss adverse events or unanticipated problems over the phone. If a patient is lost to follow-up, two phone calls to the patient and subsequently two phone calls to next-of-kin will be made in an attempt to reach the patient. There is low concern for long-term and short-term safety with either study agent, particularly for the duration of eight weeks only.

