7.2.5 Withdrawal/Early Termination Visit

If 12 weeks of study agent usage:

- Record AE as reported by participant or observed by investigator
- Record participant's adherence to treatment regimen
- Obtain GSM symptom history, and record VAS scores for dyspareunia, itching, and dryness
- Record vital signs, results of physical exam including pelvic
- Collect pelvic samples for vaginal pH and vaginal tissue scraping for vaginal maturation index
- Have patient fill out VSQ
- Discuss the obvious, preliminary changes in their symptoms, if any exist
- Provide contact information for [name] to communicate any AE or side-effect experienced after the end of the study if patient believes it is related to the study

If <12 weeks of study agent usage:

- Record AE as reported by participant or observed by investigator
- Record participant's adherence to treatment regimen
- Record vital signs, results of physical exam including pelvic
- Provide contact information for [name] to communicate any AE or side-effect experienced after the end of the study if patient believes it is related to the study

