10.3 Analysis Datasets

The analysis dataset will include the intent to treat cohort, to include all those randomized to treatment, as well as a per protocol set to include who used either the control or investigational product for at least 12 weeks.

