10.4.1 Analysis of the Primary Endpoint

- VSQ score (see attached below):
 - Definition: 21 question survey
 - Interval variable overall (binary responses; a 'yes' equates to one point, a 'no' equates to zero points for each question which is then added up to a sum)
 - Single endpoint measure with a score that can range from 0 to 21

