10.5 Sample Size

This study would be the first US-based randomized trial investigating HLA's usage for GSM treatment, to the authors' best knowledge. Thus, the sample size of 60 has been chosen to pilot the presented protocol, to assess feasibility and acceptability in quality of life for HLAs and to gather preliminary effectiveness for planning a larger effectiveness trial. The authors acknowledge the limitations of having enrolling 60 individuals, including generalizability. However in this initial stage of study implementation and design, expect this number to provide sufficient information.

No study to date has used the VSQ to assess the impact of treatment modalities for GSM, so there is no historical data to provide an assumed mean score. However, with 30 individuals randomized to each study treatment, we expect to have at least 80% probability of achieving a 95% confidence interval (CI) width of 1.7, assuming a standard deviation in the VLM of 2. With fewer individuals at any timepoint, the width of the CI will increase.

The assumed drop-out, withdrawal, cross-over and missing data rate is assumed to be 33%, which explains the enrollment goal of 60 to allow for 40 evaluable patients. This is a conservative estimate because the missing data rates in RCT's from four major journals has shown to be 20% or greater in about 18% of trials, which was also seen in quality-of-life studies (26, 27). We will monitor reasons for drop out and withdrawal of treatment to improve study adherence and follow up.

All participants will be included in the intent to treat analyses, and those participants who use the study intervention for at least 12 weeks will be included in the per-protocol analysis.

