27. National Research Council. The prevention and treatment of missing data in clinical trials. National Academies Press, 2010.

CONFIDENTIAL

This material is the property of the NYU School of Medicine and Langone Medical Center. Do not disclose or use except as authorized in writing by the study sponsor
Interventional Template Version: 11 January 2019

19 Attachments

19a The Vulvovaginal Symptom Questionnaire

The Vulvovaginal Symptom Questionnaire

The following questions were developed to assess skin symptoms of women. The skin surrounding the vagina is called the vulva. Just like skin in other parts of the body, the vulva can sometimes become irritated. Many women experience discomfort in the region of the vulva. These symptoms may be mild, but can sometimes be severe. The following questions will ask you about your vulvar skin symptoms during the past week.

During the past week, have you been bothered by:

1. Your vulva itching? No Yes
2. Your vulva burning or stinging? No Yes
3. Your vulva hurting? No Yes
4. Your vulva being irritated? No Yes
5. Your vulva being dry? No Yes
6. Discharge from your vulva or vagina? No Yes
7. Odor from your vulva or vagina? No Yes
8. Worry about your vulvar symptoms?
(for example, that it will spread, get worse, scar, etc.) No Yes
9. The appearance of your vulva? No Yes
10. Frustration about your vulvar symptoms? No Yes
11. Embarrassment about your vulvar symptoms? No Yes
12. The effects of your vulvar symptoms on your interactions with others? No Yes
13. The effects of your vulvar symptoms on your desire to be with people? No Yes
14. Your vulvar symptoms making it hard to show affection? No Yes
15. The effects of your vulvar symptoms on your daily activities? No Yes
16. Your vulvar symptoms affecting your desire to be intimate? No Yes
17. Are you currently sexually active with a partner?
 No → Thank you. You are done with this questionnaire.
 Yes → Please proceed with the next 4 questions
18. The effects of your vulvar symptoms on your sexual relationships? No Yes
19. Your vulvar symptoms causing pain during sexual activity? No Yes
20. Your vulvar symptoms causing dryness during sexual activity? No Yes
21. Your vulvar symptoms causing bleeding during sexual activity? No Yes

CONFIDENTIAL

This material is the property of the NYU School of Medicine and Langone Medical Center. Do not disclose or use except as authorized in writing by the study sponsor
Interventional Template Version: 11 January 2019

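### No week-12 VSQ is listed for women who stop early: the fallback call covers only safety, and the early-termination list for under 12 weeks of use omits the primary endpoint

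*Combined protocol and SAP*

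**What the plan says.** Section 4.2.1 defines the outcome: "The primary endpoint will be the change in the VSQ score, between the baseline visit and 12 week follow-up". Section 10.4.1 scores it from "binary responses; a 'yes' equates to one point, a 'no' equates to zero points for each question", and Attachment 19a gives the recall period: "The following questions will ask you about your vulvar skin symptoms during the past week".

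For women who withdraw, Section 5.7.2 first arranges an in-person contact: "a follow-up office visit will be set up at 12 weeks regardless of their participation". The fallback is: "If the patient refuses to come in, a phone call will be made to discuss adverse events or unanticipated problems over the phone". No efficacy item and no date is attached to that call. The section ends by citing an eight-week duration as a reason for low safety concern, whereas Sections 4.1 and 6.1.9 state 12 weeks.

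Section 7.2.5 splits the early-termination visit in two. The branch for 12 weeks of use includes the VSQ. The branch headed "If <12 weeks of study agent usage" lists adverse events, adherence, vital signs and examination, and contact information, with no questionnaire.

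On analysis, Section 10.3 states: "The analysis dataset will include the intent to treat cohort, to include all those randomized to treatment". Section 10.4 uses a linear mixed model to keep women without a 12-week value, assuming that value is missing at random. On expected loss, Section 10.5 states: "The assumed drop-out, withdrawal, cross-over and missing data rate is assumed to be 33" percent, that is, 60 enrolled for 40 evaluable.

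**The concern.** The plan promises an analysis of everyone randomised, but its data-collection rules do not ask early stoppers for the primary outcome. By either route (declining the visit, or attending under the short-use list), a woman can be in contact with staff and still leave without a VSQ. Nothing about the instrument requires this. It has at most 21 yes/no items, and a woman who is not sexually active stops at item 17. The VSI (five items in Attachment 19h) and the PGI-I (one item) are also short self-reports.

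Outcomes are taken only at baseline and week 12, so there is no intermediate score to stand in for a missing one. If women who stop differ in response from women who stay, the arm estimates describe the stayers. Sections 10.1 and 10.5 say those estimates will inform a larger trial, so the error would carry into its planning. In an open-label trial the loss could also differ by arm.

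**Working it through.** **Inputs.** From Section 10.5: 30 women per arm; SD 2 (attached to an undefined abbreviation, VLM, and taken here as the VSQ); target 95% CI width 1.7 with at least 80% probability; loss 33%. Not in the documents, so assumed: the gap g between women without a week-12 VSQ and completers (1 to 3 points), and the number r of the 20 lost women whose VSQ is recovered.

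**The plan's own figures.** Expected per-arm width = 2 × t(0.975, n−1) × SD / √n. The width met with 80% probability multiplies this by √[χ²(0.80, n−1)/(n−1)].
- n = 30: 2 × 2.045 × 2 / √30 = 1.49. The 80% width is 1.64 and P(width ≤ 1.7) = 0.87. The smallest n reaching 80% is 29, so the stated 30 reproduces.
- Enrolment: 40 / (1 − 0.33) = 59.7, or 60. This also reproduces.
- The 1.7 is a within-arm width. The between-arm difference at 30 per arm has an expected width of 2.07.

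**Error in the completers' mean.** With completers' mean change C and one third missing, the mean for all randomised women is C − g/3. If r lost women, representative of the 20, are recovered, the observed mean is C − g × r/(40 + r). The remaining error is g × (1/3 − r/(40 + r)).
- r = 0: 0.333g, or 0.33 to 1.00 point.
- r = 5: (1/3 − 5/45)g = 0.222g, or 0.22 to 0.67.
- r = 10: (1/3 − 10/50)g = 0.133g, or 0.13 to 0.40.
- r = 20: zero. This is an upper bound and not a realistic case.

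For scale, half the planned width is 1.7 / 2 = 0.85 point.

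**Precision, SD 2.**

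| Recovered of 20 | n per arm | Expected width | 80% width | P(width ≤ 1.7) |
|---|---|---|---|---|
| 0 | 20 | 1.87 | 2.10 | 0.32 |
| 5 | 22–23 | 1.77–1.73 | 1.98–1.93 | 0.43–0.50 |
| 10 | 25 | 1.65 | 1.83 | 0.62 |
| 20 | 30 | 1.49 | 1.64 | 0.87 |

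**Does the planned model fill the gap?** For a woman seen only at baseline, a mixed model can use the baseline score at most. It can correct for differences in outcome that baseline VSQ explains, but not for differences that arose during treatment. Without post-baseline data on these women, the assumption cannot be examined.

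**The case against.** The case on the other side has six parts.

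- **The plan does follow withdrawn women.** Section 5.7.2 arranges a 12-week visit, and the final-visit list in Section 7.2.4 includes the VSQ. A reader might infer that no early stopper will ever give a VSQ. The documents do not go that far, because they do not say whether that visit follows Section 7.2.4 or the short-use list in Section 7.2.5. The ambiguity itself stands, and the fallback call is not ambiguous.
- **The women are not dropped from the analysis.** This is correct. The mixed model keeps them, and Section 10.4 also summarises missing outcomes by participant characteristics. Neither supplies the missing response.
- **Not all 20 can be reached.** A reader might treat the whole 33% as recoverable. Section 10.5 pools drop-out, withdrawal, cross-over and missing data; women lost to follow-up have a separate procedure in Section 5.7.2, and cross-overs may still attend. The documents give no count of women who would refuse the visit but take the call. This stands, and is why a range is shown.
- **The direction is not known.** A reader might infer that results will look too favourable. The documents do not show that refusers improve less. Section 15.2 offers no payment or travel reimbursement, so burden is an equally plausible reason to stay away, and Section 6.1.8 allows estrogen to be stopped for side effects. This stands.
- **Consent.** Section 13.3.2 allows withdrawal of consent at any time, and Section 13.5 restricts collection after authorisation is revoked. Endpoint questions are not safety questions. This stands and limits the fix.
- **Mode of collection.** Phone scores would come only from withdrawn women and be taken by unblinded staff (Section 10.6.1), some on intimate items, and the documents do not address telephone use of the VSQ. Recording the mode documents this but does not correct it. This stands.

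**Conclusion.** The point holds as a gap in data collection that is cheap to close. As written, a woman who stops early and declines the visit has no VSQ planned, and one who attends under the short-use list has none listed. The intent-to-treat estimate then depends on an assumption the trial cannot check.

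The possible error is 0.33 to 1.0 VSQ point in an arm's completer mean at 33% loss, falling to 0.22 to 0.67 or 0.13 to 0.40 with 5 or 10 of 20 recovered. Expected per-arm CI width falls from 1.87 to about 1.73–1.77 or 1.65. These figures assume a gap of 1 to 3 points, equal loss in both arms, recovered women who are typical of those lost, and SD 2. The baseline-adjusted model would remove whatever part of the gap baseline VSQ explains.

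A reader might carry the 0.33 to 1.0 over to the HLA-versus-estrogen difference. That does not follow: equal loss and equal gaps cancel between arms, and the documents give no arm-specific loss. The per-protocol set, limited to women with at least 12 weeks of use, would not gain from scores of women who used the product for less. Section 10.1 makes this an estimation pilot without formal comparison, so the gap weakens its planning estimates but does not invalidate the trial.

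**What to change.** - **Section 5.7.2:** for women who decline the visit and still agree to provide data, make the call within the week-12 window and collect the VSQ, VSI and PGI-I together with the safety questions. State that women who have withdrawn consent or revoked authorisation are not asked.
- **Section 7.2.5:** add a week-12 VSQ to the branch for under 12 weeks of use, and say how that list relates to the 12-week visit in Section 5.7.2.
- **Timing:** Section 7.2.4 allows 3 to 5 days either side of week 12 and the Schedule of Events allows one week. Reconcile these so the call has one window.
- **Sections 10.3 and 10.4:** include the scores in the intent-to-treat analysis, record the mode of collection, and add a sensitivity analysis excluding interview-collected scores. That analysis shows how far the result depends on these scores. It cannot separate a mode effect from a true difference, because phone collection occurs only among withdrawn women.
- **Duration:** reconcile the eight weeks in Section 5.7.2 with the 12 weeks stated elsewhere.

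The cost is a few extra minutes in a call already planned, plus a few scores taken by interview by unblinded staff. No visit or examination is added.
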